#### **4.6.1            Efficacy Endpoints (Secondary Objectives)**

##### **Time to alleviation of influenza signs and symptoms**

Time to alleviation (TTAS) of influenza signs and symptoms in hours, will be summarized using descriptive statistics by treatment, as well as Kaplan-Meier plots. It is defined as the length of time taken from the start of treatment to the point at which all of the following criteria are met and remain so for at least 21.5 hours:

- A score of 0 (no problem) or 1 (minor problem) for cough and nasal symptoms (items 14 and 15 of the CARIFS questionnaire - see [Appendix 4](#))
- A “yes” response to the following question on the CARIFS: “Since the last assessment has the subject been able to return to day care/school, or resume his or her normal daily activity in the same way as performed prior to developing the flu?”
- First return to afebrile state (tympanic temperature  $\leq 37.2^{\circ}\text{C}$ ).

If a score of 4 (“do not know” or “not applicable”) occurs at any assessment during the study for items 14 or 15, the assessment will not be included in the calculation of the alleviation of symptoms because the assessment was unobservable.

Patients with symptom scores  $\leq 1$  for both items 14 and 15, as well as tympanic temperature  $\leq 37.2^{\circ}\text{C}$  and a “yes” response to the question ‘Since the last assessment has the subject been able to return to day care/school, or resume his or her normal daily activity in the same way as performed prior to developing the flu?’ at baseline will have a TTAS of all symptoms set to missing.

Patients who do not experience alleviation of symptoms prior to completion or withdrawal from study will be censored at the last observation time point.

Baseline is defined as the first CARIFS assessment after start of treatment on Day 1.

The number of patients with completed CARIFS as well as the number with missing CARIFS per assessment, will be presented by treatment. Additionally, the number and percentage of those with ‘Don’t Know/ Not Applicable’ per Question per assessment will be presented by treatment.

##### **Duration of fever**

Duration of fever will be summarized using descriptive statistics by treatment, as well as Kaplan-Meier plots. It is defined as the time to return to afebrile state [tympanic temperature  $\leq 37.2^{\circ}\text{C}$ ] and remaining so for at least 21.5 hours.

Patients who do not return to afebrile state will be censored at the last observation time point.

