#### **4.3.3 Rescue Medication**

If influenza symptoms, such as fever and headache, are so severe, in the opinion of the patient/caregiver, that the patient needs rescue therapy between Day 1 and Day 29, the use of acetaminophen at a dose appropriate to the age and weight of the child will be permitted only for the relief of fever or pain. If acetaminophen is used, the patient/parent/caregiver will record the use in the patient diary, and the investigator will record the date, time, and dose at the next visit. Acetaminophen will not be provided by the Sponsor.

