#### **4.6 EFFICACY ANALYSIS**

The statistical analyses of efficacy endpoints will be descriptive. The ITTi population will be used for all analyses. Additional analysis of efficacy analysis presenting the ITT population will not be completed.

The data will be summarized using means, standard deviations, medians, and ranges for continuous variables and proportions for categorical variables, as appropriate. Time-to-event endpoints and duration endpoints will be summarized using Kaplan-Meier plots and summaries of the median survival time. Summaries will be presented by treatment group.

Efficacy endpoints are based on the CARIFS questionnaire data which is recorded by parent/ caregiver using handheld device. This assessment data should be recorded for the following time periods:

Period	Time
Morning	0.500-10.59
Noon	11.00-14.59
Evening	15.00-18.59
Bedtime	19.00-23.59

\*data should not be recorded between 00.00 and 4.59.

In the case where the recorded time of an assessment is outside the period time window for that assessment, the end time of the period should be imputed as the assessment time.

In the case where the assessment time falls into the period between 00.00 and 4.59 (due to technical error) the assessment date will be imputed to the date prior to recorded assessment date and the assessment time will be imputed to the end time of the period time window.

The imputation method used in the derivation of time to alleviation of influenza signs and symptoms is described in Section 4.6.1. No further imputation methods will be used.

In all time to event analysis, patients who withdraw prior to event of interest will be censored at the last observation timepoint.

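### Temperatures taken after rescue acetaminophen count as afebrile, so duration of fever can be dated too early, and no planned analysis would show it

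*SAP*

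**What the plan says.** **Fever endpoints.** SAP 4.6.1 states for duration of fever: "It is defined as the time to return to afebrile state [tympanic temperature" at or below 37.2 °C, "and remaining so for at least 21.5 hours". Time to alleviation, the key secondary endpoint, requires that "all of the following criteria are met and remain so for at least 21.5 hours". One of its three criteria is "First return to afebrile state (tympanic temperature" at or below 37.2 °C; the others concern cough and nasal symptoms, and return to normal activity. Protocol Table 1 gives the same definitions. None carries a condition on antipyretic use.

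**Rescue.** Protocol 4.3.3 lets the patient or caregiver judge whether "the patient needs rescue therapy between Day 1 and Day 29". Acetaminophen "will be permitted only for the relief of fever or pain". On recording: "If acetaminophen is used, the patient/parent/caregiver will record the use in the patient diary, and the investigator will record the date, time, and dose", the last at the next visit. Protocol 4.4.3 prohibits other antipyretics.

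**Analysis of these data.** The body of the SAP does not mention acetaminophen; it appears only in the copied synopsis. SAP 4.3 plans descriptive summaries of previous and concomitant treatment by arm. SAP 4.4 cuts summaries of concomitant medication at the last exposure date. SAP 4.6 adds that "No further imputation methods will be used".

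**The concern.** Acetaminophen is the one permitted antipyretic and it acts directly on the measured variable. A reading at or below 37.2 °C after a dose may show the drug effect and not the end of fever. Because both endpoints are dated from the start of the afebrile run, a masked reading just before true recovery moves the recorded time earlier. Children with longer fever have more occasions to be medicated.

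At stake is how the Kaplan-Meier curves and medians for fever can be read. They are the trial's fever result, and nothing planned shows how much they depend on readings taken after acetaminophen, or whether use differed between arms while the diary was running.

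**Working it through.** **1. The plan's own figure.** No figure in the documents concerns the fever endpoints. The only design calculation is the adverse-event table for 80 children. At 3% incidence, 1 − 0.97^80 = 91.3%, as stated. The other four entries also reproduce. It does not use efficacy data, so the sample size is untouched.

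**2. Readings needed to span 21.5 h.** The schedule is four readings daily on Days 1–3, two on Days 4–9 and one on Days 10–15 (Protocol Appendix 1). Clock times are assumed: 08:00, 13:00, 17:00 and 21:30; then 08:00 and 17:00; then 08:00.

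| Run starts on | Consecutive readings needed |
|---|---|
| Days 1–2 | 5 |
| Day 3 | 4 or 5 |
| Days 4–9 | 3 |
| Days 10–14 | 2 |

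**3. A run masked throughout.** Suppose each febrile reading is masked independently with probability q (assumed). A given run of k readings is fully masked with probability q^k.

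| q | k = 5 | k = 3 | k = 2 |
|---|---|---|---|
| 0.5 | 3% | 13% | 25% |
| 0.7 | 17% | 34% | 49% |
| 0.9 | 59% | 73% | 81% |

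The persistence rule therefore gives real protection on the early days, when most fevers probably end.

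**4. Only the last febrile reading masked.** This needs far less. Take treatment at 10:00 on Day 1 and true fever ending at 10:00 on Day 4. The first true afebrile reading is 17:00 on Day 4, at 72 + 7 = 79 h. If the 08:00 reading that day is masked, the run starts at 72 − 2 = 70 h, 9 h early, and genuine readings complete it. In this mechanism the chance of early dating is about q, not q^k.

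**5. Effect on one arm's median.** Simulation: exponential true duration, treatment at 10:00 on Day 1, the clock times in step 2, independent masking. All of these are assumptions.

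| True median | q = 0 | q = 0.3 | q = 0.5 | q = 0.7 |
|---|---|---|---|---|
| 24 h | 27 h | 22 h | 22 h | 11.5 h |
| 48 h | 51 h | 46 h | 35.5 h | 22 h |

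With a 48 h median, the share of children dated early is 31%, 55% and 77% at q = 0.3, 0.5 and 0.7. Medians can only fall on diary slots, so they move in jumps; the share dated early is the steadier result.

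**6. Effect on the difference between arms.** Simulation: lognormal true duration (sigma 0.7), first dose uniform between 09:00 and 18:00, masking equal in both arms. True medians of 24 h and 48 h are assumed.

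| Children masked at every reading | Masking of other readings | Observed difference |
|---|---|---|
| 0 | 0 | 24.3 h |
| 10% | 0 | 22.5 h |
| 20% | 20% | 20.5 h |
| 30% | 20% | 12.5 h |
| 30% | 40% | 12.1 h |

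The step from 20.5 h to 12.5 h is largely a median crossing the overnight gap between readings. With 24 h against 28 h, an observed difference of 3.9 h falls to 2.0 h at 20%/20%. With equal true medians it stays at about 0.

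**7. Time to alleviation.** In the sponsor's Japanese paediatric study (Protocol 1.2.3), median fever resolution was 21.4 h, against 44.6 h for alleviation of cough, nasal symptoms and fever together. Fever is then often not the last criterion to resolve, and masking moves this endpoint only when it is.

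**8. Whether the concomitant-treatment summary fills the gap.** It is not linked to temperatures. SAP 4.5.6 sets baloxavir exposure at 1 day and oseltamivir exposure from first to last dose, which ends on Day 5 or 6. If those definitions set the cut-off, acetaminophen counts only on Day 1 in one arm and to Day 5 or 6 in the other. If placebo dosing counts as exposure, both arms stop at Day 5 or 6. The diary runs to Day 15 either way.

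**The case against.** The strongest reply is that counting temperatures whatever rescue was given is a legitimate treatment-policy choice, and that the SAP follows the protocol definition. That stands: the as-recorded analysis is not an error and should not be replaced. It does not explain why no supplementary look is planned when dose times are collected.

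Several stronger readings are tempting but unsupported:

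- A reader might infer that SAP 4.6 forbids any handling of these readings. The sentence rules out further imputation only; setting a reading aside is not imputation.
- A reader might infer that unequal acetaminophen use would go unreported. Acetaminophen is concomitant therapy under Protocol 4.4, and a by-arm summary is planned. The fault is its cut-off and the missing link to temperatures.
- A reader might infer a precedent in the SAP's exclusion of don't-know CARIFS answers. There no rating exists; a temperature is a measurement.
- A reader might infer that the comparison with oseltamivir is known to be diluted. The 24 h and 48 h medians have no source in the documents. The only clinical comparison of the two drugs they report is in adults: 53.5 h against 53.8 h to alleviation of symptoms, not significantly different.

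A supplementary rule also has its own errors. Acetaminophen may be given for pain, so some readings set aside would be genuinely afebrile. The investigator records dose times at visits on Days 2, 4, 6, 10 and 29, so some may be recalled.

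**Conclusion.** The gap is real and limited. Duration of fever can be dated too early when the last febrile readings before recovery follow acetaminophen, and the 21.5-hour rule reduces this without removing it. Time to alleviation shares the weakness only when fever resolves last.

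The documents give neither a rate of acetaminophen use nor a duration of its effect, so the size and the between-arm direction cannot be stated. The figures above are illustrations under assumed durations, diary times and masking rates. Equal true medians with equal masking give no between-arm bias; if use differed, the arm with more masking would look better on fever.

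Both endpoints are secondary and descriptive, with no test or margin. The primary safety objective and the sample size are unaffected. This is a modest improvement and does not invalidate the plan.

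**What to change.** Leave the rescue rules, the protocol definitions and the as-recorded analysis as they are. In SAP 4.6.1, before unblinding, add:

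1. A supplementary analysis of duration of fever, and of the fever criterion of time to alleviation. Readings at or below 37.2 °C within a stated interval after recorded acetaminophen neither start nor confirm the afebrile run; readings above 37.2 °C still count as fever. The sponsor should choose and justify the interval, and say how a dose with no usable time is treated.
2. A repeat with a second interval, both shown beside the as-recorded result.
3. A table of children using acetaminophen and number of doses, by arm and day over Days 1–15, exempt from the last-exposure cut-off in SAP 4.4.

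The cost is SAP wording, one derived flag and two or three outputs from data already collected. The downside is that some genuine afebrile readings become non-evaluable, so medians in the supplementary analysis may be longer and a few more children censored. Showing it beside the as-recorded analysis lets the reader see how far the result depends on the rule.

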## **Duration of symptoms**

Duration of symptoms will be summarized using descriptive statistics by treatment, as well as Kaplan-Meier plots. Duration of symptoms is defined as alleviation of all symptoms as defined by a score of 0 [no problem] or 1 [minor problem] and remaining so for at least 21.5 hours, for all 18 symptoms specified in the CARIFS questionnaire.

If a score of 4 (“do not know” or “not applicable”) occurs at any assessment during the study for any item, with the exception of items 10, 11 and 12 the assessment will not be included in the calculation of the alleviation of symptoms because the assessment was unobservable.

However, if a score of 4 occurs for items 10, 11 or 12, the assessment will be included, with a score of missing for these items.

In addition, duration of individual symptoms will be summarized using descriptive statistics by treatment, as supportive analysis. Patients who have an individual symptom score  $\leq 1$  at baseline will have the duration of that symptom set to missing.

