#### **4.1.1 Inclusion Criteria**

Patients must meet the following criteria for study entry:

- Written informed consent/assent for study participation obtained from patient's parents or legal guardian, with assent as appropriate by the patient, depending on the patient's level of understanding
- Aged 1 to <12 years at randomization (Day 1)
- Parent/guardian willing and able to comply with study requirements, in the investigator's judgment
- Patient able to comply with study requirements, depending on the patient's level of understanding
- Patient with a diagnosis of influenza virus infection confirmed by the presence of all of the following:
  - Fever  $\geq 38^{\circ}\text{C}$  (tympanic temperature) at screening
  - At least one respiratory symptom (either cough or nasal congestion)

- The time interval between the onset of symptoms and screening is  $\leq 48$  hours (the onset of symptoms is defined as the time when body temperature first exceeded 37.5°C if known, or the time when the first symptom was noticed by patient, parent, or caregiver)

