## Canadian Acute Respiratory Illness and Flu Scale (CARIFS) Questionnaire

Item	No Problem	Minor Problem	Moderate Problem	Major Problem	Don't Know/Not Applicable
1. Poor appetite .....					
2. Not sleeping well					
3. Irritable, cranky, fussy.....					
4. Feels unwell .....					
5. Low energy, tired .....					
6. Not playing well.....					
7. Crying more than usual .....					
8. Needing extra care .....					
9. Clinginess.....					
10. Headache.....					
11. Sore throat.....					
12. Muscle aches or pains .....					
13. Fever .....					
14. Cough.....					
15. Nasal congestion, runny nose.....					
16. Vomiting .....					
17. Not interested in what's going on					
18. Unable to get out of bed.....					

Since the last assessment has the subject been able to return to day care/school, or resume their normal daily activity in the same way as performed prior to developing the flu?  Yes  No

This form was filled out by:

- Parent
- Carer
- Other

Note: The term "Carer" in this questionnaire corresponds to the term "caregiver" used throughout the protocol.

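### Duration of symptoms: a child with any one of 15 CARIFS items answered as unknown or not applicable throughout has no usable assessment and cannot have the event, even when recovered

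*SAP*

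**What the plan says.** The CARIFS form (Protocol Appendix 3, SAP Appendix 4) has one response column, "Don't Know/Not Applicable", for two different answers. The SAP codes it as 4.

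SAP 4.6.1 has two rules for that code:

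- **Duration of symptoms.** The event requires scores of 0 or 1, "remaining so for at least 21.5 hours, for all 18 symptoms specified in the CARIFS questionnaire". A score of 4 on any item removes the whole assessment, except for headache, sore throat and muscle aches ("with the exception of items 10, 11 and 12 the assessment will not be included in the calculation of the alleviation of symptoms"). For those three items "the assessment will be included, with a score of missing for these items".
- **TTAS.** The symptom criterion is "A score of 0 (no problem) or 1 (minor problem) for cough and nasal symptoms (items 14 and 15 of the CARIFS questionnaire", combined with temperature and the return-to-activity question. A score of 4 removes the assessment only "for items 14 or 15, the assessment will not be included in the calculation of the alleviation of symptoms because the assessment was unobservable".

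SAP 4.6 allows no imputation beyond what it and 4.6.1 describe. Its general censoring rule covers patients who withdraw before the event. The TTAS text adds a rule for completers without alleviation (censoring at the last observation time point). The Duration of symptoms text adds none.

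**The concern.** Declaring a single unanswerable assessment unobservable is reasonable. The difficulty arises when an item is answered 4 for the whole illness, because then every assessment is removed and no 21.5-hour run can be found.

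Such answers are conceivable in children aged 1 to under 12. A caregiver may regard items 7 (crying more than usual) or 9 (clinginess) as not applicable to an 11-year-old. Cough or nasal symptoms may be marked that way in a child who never had one of them, since entry needs only "At least one respiratory symptom (either cough or nasal congestion").

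A recovered child would then enter the Kaplan-Meier curve as a non-event, or leave the analysis, because of the response option chosen. The SAP accepts for items 10 to 12 that a score of 4 need not void the form, and gives no reason for stopping there. About 40 children are planned on oseltamivir, fewer in the influenza-infected (ITTi) population, so a few such children could move that arm's median.

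**Working it through.** The plan states no figure on this point, so there is none to reproduce. The check has two parts.

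**1. Apply the two rules to a child with one item always scored 4.** The schedule (SAP Appendix 2) is twice daily on Days 1-9 and once daily on Days 10-15: 9 × 2 + 6 × 1 = 24 nominal assessments.

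| Item always scored 4 | Number of items | Usable for Duration of symptoms | Usable for TTAS |
|---|---|---|---|
| 1-9, 13, 16-18 | 13 | 0 of 24 | 24 of 24 |
| 14, 15 | 2 | 0 of 24 | 0 of 24 |
| 10-12 | 3 | 24 of 24 (item set to missing) | 24 of 24 |

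So 13 + 2 = 15 items can block Duration of symptoms and 2 can block TTAS. Duration of fever uses temperature alone, and return to normal health and activity uses one yes/no question. Neither has a score-4 rule.

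**2. Effect on a median.** The share of children affected, f, is not in the documents, so a range is assumed. Suppose blocked children stay at risk past the median and the others have true survival function S(t). The reported median is then the time at which

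0.5 = f + (1 − f)·S(t), so S = (0.5 − f)/(1 − f).

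The ratio to the true median is −ln(S)/ln(2) for exponential times and exp(0.7·Φ⁻¹(1 − S)) for lognormal times with log-SD 0.7. Both shapes are assumptions.

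| f | S | Exponential | Lognormal | Children in an arm of 40 |
|---|---|---|---|---|
| 5% | 0.45/0.95 = 0.474 | 0.747/0.693 = 1.08 | exp(0.7 × 0.066) = 1.05 | 2 |
| 10% | 0.40/0.90 = 0.444 | 0.811/0.693 = 1.17 | exp(0.7 × 0.140) = 1.10 | 4 |

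The median is inflated by about 5-8% at f = 5% and 10-17% at f = 10%.

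If blocked children are instead excluded or censored at time zero, they never contribute to the risk set and this inflation does not arise. The cost is then lost patients: at f = 10%, 4 of 40 on oseltamivir and 8 of 80 on baloxavir marboxil, before the reduction to ITTi.

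The SAP does not settle which case applies. For Duration of symptoms, no rule covers a completer without the event. For TTAS there is a rule, but not whether a removed assessment counts as an observation when the last one is identified.

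**The case against.** The strongest reply is that the scenario is assumed. Every item offers a no-problem answer, which scores 0 and meets the criterion. A caregiver of a child who never coughs, or of an older child who is not clingy, can simply choose it. Harm requires the other column at every assessment, and nothing in the documents shows how often that happens. The entry criterion shows that cough or nasal congestion may be absent, not that absence is coded 4. Items 10 to 12 are symptoms a small child may be unable to report, so exempting only those may be deliberate. All of this stands: the frequency is unknown and may be small.

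It is also fair that efficacy is secondary and descriptive, that caregivers answer under double-blind treatment, and that the SAP will tabulate score-4 answers. That table, however, is per question and per assessment, so it will not show which children are blocked throughout.

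A reader might infer three stronger things that the documents do not support:

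- **That all symptom endpoints, or TTAS through all 15 items, are affected.** The broad rule belongs to Duration of symptoms. TTAS is blocked only through items 14 and 15.
- **That medians will be inflated.** This holds only if blocked children stay at risk past the median. Nor can the 44.6-hour median of the Japanese paediatric study (Protocol 1.2.3) be scaled up to give hours here, because it comes from a differently defined endpoint.
- **That the comparison is biased towards one arm.** No mechanism for a systematic difference is shown; a chance imbalance is possible.

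**Conclusion.** The point holds for Duration of symptoms. As written, the rule makes the event unreachable for a child with any one of 15 items scored 4 throughout, whatever the child's recovery. It holds for TTAS only through cough and nasal symptoms.

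The size depends on an unknown f and on an unstated handling rule: 5-8% on the median at f = 5% and 10-17% at f = 10% if blocked children stay at risk, or loss of those patients if they are excluded or censored at time zero. The percentages assume that blocked children otherwise resemble the rest.

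Because the endpoints are descriptive, this does not threaten the trial's primary safety objective. It should still be corrected: the current rule can misclassify recovered children, and the Duration of symptoms text leaves completers without the event undefined.

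**What to change.** In SAP 4.6.1, before unblinding:

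1. **Duration of symptoms.** If an item is never scored 2 or 3 for a child and is scored 4 at an assessment, keep the assessment, treat that item as non-contributing, and judge alleviation on the remaining items. This does not depend on the item being scored 4 every time, so one stray 0 or 1 does not defeat it.
2. **Missing items.** State that a non-contributing or missing item, including items 10 to 12, does not block the 0/1 criterion. The present text leaves this open against the all-18-symptoms definition.
3. **TTAS.** Apply the same rule to item 14 or 15, provided the other of the two is scored at that assessment, so that no child is declared alleviated on temperature and activity alone.
4. **Existing exclusion.** Outside items 10 to 12, which keep their present exemption, remove the whole assessment when an item scored 4 was scored 2 or 3 at some other assessment of that child.
5. **Censoring.** State how a completer without the event is censored for Duration of symptoms, and whether a child with no scorable assessment is censored (and when) or excluded.
6. **Sensitivity analysis.** Report the current rule alongside.

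The cost is SAP wording, a derivation flag and one extra analysis on data already collected. The downside is that a persistent unknown is treated as symptom absent, because the form does not separate it from not applicable. The sensitivity analysis shows how much the results depend on that.
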